For all tables below, the study coordinating center at HPHCI will receive Data Partner-specific tables (there will be one of each table per Data Partner). The coordinating center will generate aggregated tables for Data Partners (shown below), these will be shared with the Duke DCC statistical team. Duke DCC will have a data-use agreement with each Data Partner as necessary in order to receive/access aggregate summary data, which are housed at HPHCI. Duke DCC will conduct the meta-analysis across all study sites. No Data Partner-specific tables will be shared beyond the coordinating center and Duke DCC, if agreed upon by Data Partners, the analytic team; only data aggregated across sites will be published or made public.

Table A. Baseline covariates to be adjusted in the models described in sections II.C, II.D.1, II.D.2, II.D.3, and II.D.4

Demographics
Age (restricted cubic spline terms)
Sex (male vs. female)
Medical history
History of anemia (yes vs. no)
History of hypertension (yes vs. no)
History of diabetes (yes vs. no)
History of hospitalization for any bleeding (yes vs. no)
History of peripheral vascular disease (yes vs. no)
History of prior cerebrovascular disease (yes vs. no)
History of heart failure (yes vs. no)
History of kidney disease (yes vs. no)
History of MI
History of CABG
History of coronary stent
Bleeding risk score: ATRIA score (Low (≤ 3) vs. Intermediate (4) vs. High (≥ 5))
Hospitalization in the prior 6 months (0 vs. 1 vs. 2 vs. ≥ 3)

Table 1. Baseline characteristics of all patients in the modified intention to treat (mITT) analysis by early intervention vs. delayed intervention

	Overall (N=XXXX)	Early intervention (N=XXXX)	Delayed intervention (N=XXXX)	p- value	Stand. mean difference (%)
Demographics					
Age					
N					
Mean (SD)					
Median (Min, 25 th , 75 th , Max)					

	Overall (N=XXXX)	Early intervention (N=XXXX)	Delayed intervention (N=XXXX)	p-value	Stand. mean difference (%)
30-34 yr, %					
35-39, %					
40-44, %					
45-49, %					
50-54, %					
55-59, %					
60-64, %					
65-69, %					
70-74, %					
75-79, %					
≥ 80, %					
Sex					
N					
Female, %					
Region					
New England, %					
Mid-Atlantic, %					
South-Atlantic, %					
Midwest, %					
Mountain, %					
Pacific, %					
Unknown, %					
Medical history					
History of anemia?					
N					
Yes, %					
History of hypertension?					
N					
Yes, %					
History of diabetes?					
N					
Yes, %					
History of hospitalization for any bleeding?					
N					
Yes, %					
History of peripheral vascular disease?					
N					
Yes, %					
History of prior cerebrovascular disease?					
N					
Yes, %					

	Overall (N=XXXX)	Early intervention (N=XXXX)	Delayed intervention (N=XXXX)	p-value	Stand. mean difference (%)
History of heart failure?					
N					
Yes, %					
History of kidney disease?					
N					
Yes, %					
History of MI					
N					
Yes, %					
History of CABG					
N					
Yes, %					
History of coronary stent					
N					
Yes, %					
CHA ₂ DS ₂ VASc score					
N					
Mean (SD)					
Median (25th, 75th)					
0, %					
1, %					
2, %					
3, %					
4, %					
5, %					
6, %					
7, %					
8, %					
9, %					
Bleeding risk score: ATRIA score					
Low (≤ 3), %					
Intermediate (4), %					
High (≥ 5), %					
Hospitalization in the prior 6 months					
0, %					
1, %					
2, %					
≥ 3 , %					
Mean (SD) follow up time					
Minimum follow up time					
Maximum follow up time					
Median follow up time (range across sites)					

For Tables 2 through 9: The SAP workplan(s) run at each Data Partner sites will generate Partner-specific tables of events (per outcome, for early vs delayed intervention) and unadjusted and adjusted model results. These will be returned to the coordinating center; results will be aggregated and meta-analyses will be run on site-specific models to generate final aggregated results.

Table 2a. Odds ratio of filling at least one OAC dispensing or 4 or more INRs (primary endpoint) over the course of the 12-months of follow-up: early intervention vs. delayed intervention in the modified intention to treat (mITT) analysis

	Early Intervention, n/N (%)	Delayed Intervention, n/N (%)	Unadj. Parameter Estimate (SE)	Unadj. Odd Ratio (95% CI)	Adj. Parameter Estimate (SE)	Adj. Odds Ratio (95% CI)	p-value for adjusted OR
OAC dispensing or ≥ 4 INRs at 365 days							
No. who met endpoint due to OAC							
No. who met endpoint due to 4 INRs							
No. who met endpoint due to other code							
No. who met due to 4 INR test PX codes (CPT)							

Table 2b. Odds ratio of filling at least one OAC dispensing or 4 or more INRs (primary endpoint) by varying windows of time (42, 90, and 183 days): early intervention vs. delayed intervention in the modified intention to treat (mITT) analysis

	Early Intervention, n/N (%)	Delayed Intervention, n/N (%)	Unadj. Parameter Estimate (SE)	Unadj. Odd Ratio (95% CI)	Adj. Parameter Estimate (SE)	Adj. Odds Ratio (95% CI)	p-value for adjusted OR
OAC dispensing or first of 4 INRs at 42 days							
OAC dispensing or first of 4 INRs at 90 days							
OAC dispensing or first of 4 INRs at 183 days							

Table 2c. Odds ratio of filling at least one OAC dispensing or 4 or more INRs (primary endpoint) over the course of the 12-months of follow-up: early intervention vs. delayed intervention, by age, sex, and CHADS-VASC score in the modified intention to treat (mITT) analysis

	Early Intervention, n/N (%)	Delayed Intervention, n/N (%)	Unadj. Parameter Estimate (SE)	Unadj. Odd Ratio (95% CI)	Adj. Parameter Estimate (SE)	Adj. Odds Ratio (95% CI)	p-value for adjusted OR
OAC dispensing or first of 4 INRs – by sex							
Female							
Male							
OAC dispensing or first of 4 INRs – by age							
≤64 yrs							
65-74 yrs							
75-84 yrs							
≥85 yrs							
OAC dispensing or first of 4 INRs – by CHADS-VASC							
2-3							
4-5							
≥6							

Table 3. Hazard ratio of at least one OAC dispensing or 4 or more INRs (primary endpoint) at 12 months: early intervention vs. delayed intervention in the modified intention to treat (mITT) analysis

	Early Intervention, Cumulative incidence (95% CI)	Delayed Intervention, Cumulative incidence (95% CI)	Parameter Estimate (SE)	Hazard Ratio (95% CI)	p-value
OAC dispensing or first of 4 INRs at 365 days					
Met endpoint due to OAC					
Met endpoint due to 4 INRs					
Met due to 4 INR test PX codes (CPT)					
Met endpoint due to other code					

Kaplan Meier curves will be generated for analyses related to Table 3.

Table 4. Numbers and proportions of filling at least one OAC dispensing or 4 or more INRs (primary endpoint) over the course of the 12-months of follow-up in intervention arm: patients with provider letter vs. patients without provider letter in the modified intention to treat (mITT) analysis

	Patients with Provider Letter, n/N (%)	Patients without Provider Letter, n/N (%)	p-value
OAC dispensing or 4 INRs at 365 days			

Table 5. Proportion of days on an OAC during all follow up time, among those treated for at least 1 day: early intervention vs. delayed intervention in the modified intention to treat (mITT) analysis

	Early Intervention	Delayed Intervention	p-value
Total number			
Number of days on an OAC			
Mean (SD)			
Median			
Minimum			
25 th percentile			
75 th percentile			
Maximum			
Number of OAC dispensings			
Mean (SD)			
Median (Min, 25 th , 75 th , Max)			
Minimum			

25 th percentile			
75 th percentile			
Maximum			
Mean proportion of days on an OAC			
Standard deviation			
Median proportion of days on OAC (range across sites)			
25 th percentile			
75 th percentile			
Proportion in each arm with ≥80% of follow up time covered by an OAC episode			

Table 6. Proportion of patients actively on OAC at the end of follow-up among those treated for at least 1 day: early intervention vs. delayed intervention in the modified intention to treat (mITT) analysis

	Early Intervention, n/N (%)	Delayed Intervention, n/N (%)	Parameter Estimate (SE)	Odds Ratio (95% CI)	p-value
Actively on OAC at the end of follow-up					

Table 7. Cumulative incidence of clinical endpoints during all follow up: early intervention vs. delayed intervention in the modified intention to treat (mITT) analysis

With / without Principal Discharge Diagnosis (PDX) Flag	Outcomes	Early Intervention, n/N (%)	Delayed Intervention, n/N (%)	Early Intervention, Cumulative incidence (95% CI)	Delayed Intervention, Cumulative incidence (95% CI)	p-value
Principal Discharge Diagnosis (PDX Flag) Only	Hospitalization for ischemic stroke or unknown stroke					
	Hospitalization for transient ischemic attack					
	Hospitalization for systemic embolism					
	Hospitalization for ischemic stroke, TIA, or systemic embolism					

With / without Principal Discharge Diagnosis (PDX) Flag	Outcomes	Early Intervention, n/N (%)	Delayed Intervention, n/N (%)	Early Intervention, Cumulative incidence (95% CI)	Delayed Intervention, Cumulative incidence (95% CI)	p-value
	Hospitalization for hemorrhagic stroke					
	Hospitalization for ischemic or hemorrhagic stroke					
	Hospitalization for ischemic or hemorrhagic stroke or systemic embolism					
	Hospitalization for any bleeding					
	Composite of ischemic stroke, hemorrhagic stroke, systemic embolism and hospitalization for any bleeding					
Ignore Principal Discharge Diagnosis (PDX) Flag	Hospitalization for ischemic stroke or unknown stroke					
	Hospitalization for ischemic stroke or transient ischemic attack					
	Hospitalization for systemic embolism					
	Hospitalization for ischemic stroke, TIA, or systemic embolism					
	Hospitalization for hemorrhagic stroke					

With / without Principal Discharge Diagnosis (PDX) Flag	Outcomes	Early Intervention, n/N (%)	Delayed Intervention, n/N (%)	Early Intervention, Cumulative incidence (95% CI)	Delayed Intervention, Cumulative incidence (95% CI)	p-value
	Hospitalization for ischemic or hemorrhagic stroke					
	Hospitalization for ischemic or hemorrhagic stroke or systemic embolism					
	Hospitalization for any bleeding					
	Composite of ischemic stroke, hemorrhagic stroke, systemic embolism and hospitalization for any bleeding					
	All-cause in-hospital death [PDX flag not applicable]					

Kaplan Meier curves will be generated for analyses related to Table 7.

Table 8. Hazard ratio of each outcome: early intervention vs. delayed intervention in the modified intention to treat (mITT) analysis

With / without Principal Discharge Diagnosis (PDX) Flag	Outcomes	Early Intervention, n/N (%)	Delayed Intervention, n/N (%)	Parameter Estimate (SE)	Unadj. Hazard Ratio (95% CI)	Adj. Hazard Ratio (95% CI)	p-value for adjusted HR
Principal Discharge Diagnosis (PDX Flag) Only	Hospitalization for ischemic stroke or unknown stroke						

	Hospitalization for TIA						
	Hospitalization for systemic embolism						
	Hospitalization for ischemic stroke, TIA, or systemic embolism						
	Hospitalization for hemorrhagic stroke						
	Hospitalization for ischemic or hemorrhagic stroke						
	Hospitalization for ischemic or hemorrhagic stroke or systemic embolism						
	Hospitalization for any bleeding						
	Composite of ischemic stroke, hemorrhagic stroke, systemic embolism and hospitaliz						

	ation for any bleeding						
Ignore Principal Discharge Diagnosis (PDX) Flag	Hospitalization for ischemic stroke or unknown stroke						
	Hospitalization for TIA						
	Hospitalization for systemic embolism						
	Hospitalization for ischemic stroke, TIA, or systemic embolism						
	Hospitalization for hemorrhagic stroke						
	Hospitalization for ischemic or hemorrhagic stroke						
	Hospitalization for ischemic or hemorrhagic stroke or systemic embolism						
	Hospitalization for any bleeding						

	Composite of ischemic stroke, hemorrhagic stroke, systemic embolism and hospitalization for any bleeding						
	All-cause in-hospital death						

Kaplan Meier curves will be generated for analyses related to Table 8.

Clinical endpoints for Table 8 will be based only on diagnoses that are the principal discharge diagnoses.

Table 9. Health care utilization during all follow up time: early Intervention vs. delayed Intervention in the modified intention to treat (mITT) analysis

	Early Intervention	Delayed Intervention	p-value
Total patients	N =	N =	NA
Total encounters			
Total # of encounters per arm (N)			NA

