S₂	Prior stroke or TIA or thromboembolism	ICD-10-CM: I60.**, I60.2, I60.4, I60.6-I60.9, I61.*, I62.9, I63.0*, I63.0**, I63.1*, I63.1**, I63.2*, I63.2**, I63.3*, I63.3**, I63.4*, I63.4**, I63.5*, I63.5**, I63.6, I63.8, I63.9, I69.00, I69.0**, I69.10, I69.1**, I69.30, I69.3**, I69.8** except I69.898, I69.9** except I69.998, S06.34, S06.34*A, and S063.34*D, S06.35, S06.35*A, and S063.35*D, S06.36, S06.36*A, and S063.36*D, S06.6, S06.6X*A, S06.6X*D, Z86.73, H34.00, H34.219, H34.239, H34.9, I67.82, I74.**, I74.2-I74.9, K76.3, N28.0, T81.718A, G45.8, G45.9; ICD-9-CM: 438.0-438.8, 852.0, 853.0, 433.*1, 434.*1, 438.1*, 438.2*, 438.3*, 438.4*, 438.5*, 438.81-428.85, 852.0*, 853.0*, V12.54, 444, 444.*, 444.**, 453.9, 573.4, 362.30-362.34, 434.00, 435, 435.8, 435.9; CPT: 34101, 34111, 34201, 34203
V	Vascular disease (e.g. peripheral artery disease, myocardial infarction, aortic plaque)	ICD-10-CM²: E08.51, E08.52, E09.51, E09.52, E10.51, E10.52, E11.51, E11.52, E13.51, E13.52, I21.0*, I21.1*, I21.2*, I21.3, I21.4, I22.*, I25.7, I25.70-I25.73, I25.70*, I25.71*, I25.72*, I25.73*, I25.79, I25.79*, I25.810, I73.8, I73.9, I77.1, T82.2, T82.21 and subcodes, Z95.820, Z95.82
A	Age 65–74 years	
Sc	Sex category (i.e. female sex)	

Patients are excluded if they meet any of the following criteria:

1. Evidence of OAC medication fill during the 12 months prior to randomization (the delayed intervention group’s treatment status will be assessed at the end of the 12-month follow-up period)

² Only ICD-10-CM codes are presented for the vascular disease component given size of the list; complete code list, which includes ICD-9-CM, ICD-10-PCS, ICD-9-PCS, CPT, and HCPCS codes, is available on the [Sentinel website](#).

2. Conditions other than AF that require anticoagulation such as ever having mechanical prosthetic valve, deep venous thrombosis, or pulmonary embolism prior to the last date in the current approved data used for cohort identification (“ever” is operationalized as -6000 days from the index AF code)
3. Pregnancy identified within 6 months of the last date in the current approved data used for cohort identification
4. Any known history of intracranial hemorrhage prior to the last date in the current approved data used for cohort identification
5. Hospitalization for any bleeding within the last 6 months of the last date in the current approved data used for cohort identification

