6. Patients with recent P2Y12 antagonist use (i.e., clopidogrel, prasugrel, or ticagrelor within 90 days of prior to randomization)

F. STUDY DESIGN AND DURATION

As described in detail in the protocol, the study is a prospective, randomized, and open-label educational intervention trial. Patients with AF and a CHA₂DS₂-VASc score of 2 or greater were randomized in a 1:1 ratio to an early intervention cohort and a delayed intervention cohort within each participating health plan. The definition for OAC medication fill was an OAC medication dispensing or at least 4 INR tests in the claims data.³ The claims records of the patients randomized to the early intervention cohort were then linked to “fresh” (i.e., about 1 month old) pharmacy claims data at the time of randomization. Patients without evidence of an OAC medication fill during the 12 months prior to randomization were included in the patient-level and provider-level early educational intervention (patients randomized to this early intervention with evidence of an OAC medication fill during the 12 months prior to randomization were excluded from the trial). In addition to usual care, these patients and their providers received a one-time mailing at trial start. There were two waves of mailing for the early intervention cohort at most sites due to the practical challenges of claims data: the patients were assigned to wave 1 if they had a provider easily identified in the data (i.e., the provider associated with the most recent AF diagnosis is indeed an individual provider), and they were assigned to wave 2 if it was difficult to identify a provider (e.g., the first identified provider is actually a facility). Follow-up time started on the date of the respective wave 1 and wave 2 mailings for the early intervention patients.

The delayed intervention cohort will have received usual care over the initial study period. After the date on which at least 80% of all eligible study participants have at least 12 months of follow-up time, the treatment status of the delayed intervention group will be assessed via the Sentinel data available at that time, in addition to “fresh” pharmacy claims data. The providers of patients in the delayed cohort who did not receive OAC medication during the course of follow-up and still meet all inclusion criteria will receive the provider-only education intervention (patients will not receive the educational materials unless no provider can be identified for a mailing).

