[figure not shown]
Details on the analyses are provided in Section II. Here we describe the data sources for the **modified intention-to-treat** (primary) and **as-randomized** (sensitivity) analyses. Similar to early intervention cohort, the patients in the delayed intervention cohort will be assigned to wave 1 or wave 2 (“pseudo”

³Not all OAC dispensings are captured in pharmacy claims, particularly, for warfarin due to some patients paying for medication out of pocket. INR tests are assumed indicative of OAC fills that were not billed through the claims. Four INR tests or values within a 12-month period will be used as a proxy since that is roughly the number of tests administered in the process of stabilizing dose.

wave assignments) depending on the difficulty in identifying the patient's provider (the intent is to handle them the same way as was done for the early intervention arm, for the modified intention-to-treat analysis). The follow-up for the delayed intervention patients will start on the date the wave 1 or 2 mailings took place for a given Data Partner's early intervention cohort. For both early and delayed intervention cohorts, any patients who die, are disenrolled, or get started on OAC between the randomization and early intervention mailing will be excluded from the analysis at each Data Partner. For both the early and delayed arms, exclusion criteria that are based on member medical history were assessed at the time of randomization. For the early intervention cohort, enrollment and treatment status were assessed at randomization for all and re-assessed at the wave 2 time point at some of the sites (this was at site discretion, in response to the lag between wave 1 and 2 mailings). The enrollment and treatment status of the delayed intervention cohort will be examined for eligibility at the same time point as the early intervention patients, meaning at the time of mailing per Data Partner, via the locked data (using the wave 1 and 2 dates).

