1. 33% OAC initiation rate in the delayed intervention arm
2. 38% OAC initiation rate in the early intervention arm (5% absolute improvement in OAC initiation over the 33% OAC initiation expected in the delayed intervention arm over 1-year follow-up)
3. 1-year attrition rate: 30% dropout or lost-to-follow-up
4. Two-sided type I error rate of 0.05
5. Roughly 10,000 patients who meet the inclusion/exclusion criteria will yield more than 99% power to detect a 5% absolute difference

Power	Total sample size (2-arm)	Early Intervention	Delayed Intervention
90%	5610	2805	2805
95%	6910	3455	3455
99%	9718	4859	4859

2. Important Secondary Outcome of Stroke or TIA

A study with approximately 80,000 patients could provide reasonable power for stroke or TIA outcome under certain assumptions listed below:

- 1-year stroke or TIA rate: 18% among patients not treated with OAC
- 1-year stroke or TIA rate: 7% among patients treated with at least 1 OAC fill
- Duration of follow-up: 1 year
- 33% of delayed intervention patients will have at least 1 fill of OAC, meaning the 1-year stroke or TIA rate in the delayed intervention group would be 14.4%
- 1-year attrition rate: 30% dropout or lost-to-follow-up
- Two-sided type I error of 0.05
- If 38% of early intervention patients have at least 1 fill of OAC (meaning the 1-year stroke or TIA rate in the early intervention group would be 13.82%, i.e., an absolute reduction of 0.55%), the study will have 46% power to detect this 0.55% reduction. However, if 40.5% of early intervention patients have at least 1 fill of OAC (meaning the 1-year stroke or TIA rate in the

early intervention group would be 13.54%, i.e., an absolute reduction of 0.83%), the study will have 80% power to detect this 0.83% reduction.

8. The sample size has 80% power to detect a 0.5% absolute reduction in stroke, assuming a cumulative 1-year incidence of stroke of 4.2% in control (delayed intervention arm) patients and 3.7% in intervention (early intervention arm) patients. The assumption is that patients not on oral anticoagulation have an annual stroke rate of 5%, and stroke will be reduced by 50% (HR=0.5) in the treated (anticoagulated) population. The 80% power requires that 52% of early intervention arm patients are treated at 1-year as compared to 33% in the control arm.

II. STATISTICAL ANALYSIS

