All possible person-time will be used to assess participants’ outcomes. For the time-to-event analysis, patients will be censored from the analysis at the time of death, disenrollment from the health plan, loss of medical or pharmacy coverage, or change in eligibility for inclusion in research based on health plan membership.

[figure not shown]
Providers may have more than 1 patient in the study – either within the same arm or in both the early and delayed intervention arms. The frequency of this, when provider overlap can be identified, will be reported descriptively and it is expected to be a low proportion of whole population. Depending on the number of patients in this scenario, a sensitivity analysis may be considered to examine the effect.

There were a few variations in the implementation of the early intervention across the Data Partners due to pragmatic issues. The intervention per the protocol is targeted at both member and provider (i.e., the provider who gave most recent AF diagnosis). If the AF provider was a facility in the source data, the educational intervention was applied to the member only, unless the site chose an alternate provider. In the latter case, the intervention was sent to both the member and the alternate provider. The number of patients in each of these variations to the intended intervention will be reported.

A detailed Consort flow diagram will be provided showing the number of patients randomized to the early and delayed intervention groups, the numbers of subjects lost to follow up or excluded from analyses, and the number of subjects evaluable for the key study endpoints (Figure 1).¹

All analyses will be conducted using SAS version 9.4 or higher software (SAS Institute Inc., Cary, NC). However, version and modules to be used could vary from one Data Partner to another. All tests will be two-sided and a p-value of <0.05 will be considered statistically significant. No multiplicity adjustment will be made.

Figure 1. Consort Flow Diagram

A. METHODS FOR ANALYSIS IN DISTRIBUTED DATA NETWORKS

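### The primary model's covariate list leaves out mailing wave and earlier OAC use, two baseline variables available in both arms; the expected loss is modest

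*SAP*

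**What the plan says.** SAP II.C makes the adjusted logistic model the primary analysis. Its covariates are in SAP Appendix A, Table A, headed "Baseline covariates to be adjusted in the models described in sections II.C, II.D.1, II.D.2, II.D.3, and II.D.4". They are age (spline), sex, eleven medical-history items, ATRIA bleeding-risk category, and hospitalizations in the previous 6 months. Mailing wave and OAC dispensing before the 12-month exclusion window are not listed there, nor in baseline Tables 1 and 1S.

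On wave, SAP I.F puts early-arm patients in wave 1 when the provider at the latest AF diagnosis is an individual; otherwise, "they were assigned to wave 2 if it was difficult to identify a provider". Delayed-arm patients receive a pseudo-wave on the same basis. Follow-up in both arms starts on that wave's mailing date at the Data Partner.

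On who is analysed, SAP I.F says that early-arm enrollment and treatment status was checked at randomization and "re-assessed at the wave 2 time point at some of the sites (this was at site discretion"). The same section excludes, in both arms, anyone who died, disenrolled or started OAC between randomization and mailing. SAP II then requires early-arm members to have been mailed a letter and delayed-arm members to be untreated on the matching date. It adds that delayed-arm addresses were not assessed at that time and cannot be reconstructed.

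**The concern.** Wave is a design variable. It comes from provider data that precede randomization, fixes time zero in both arms, and is related to who can be mailed. When the AF provider is a facility, SAP II says the mailing goes to the member alone unless the site picks an alternate provider. Wave may also predict the outcome. Patients seen at facilities may differ from others, and if follow-up runs to a common cut-off date, wave 2 patients have less time to fill a prescription.

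Earlier OAC use is a plausible strong predictor of restarting and can be read from the same claims wherever look-back allows.

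Two things are at stake. The first is precision left unused. The second is a possible shift in the primary comparison if the early-arm mailing requirement, which has no delayed-arm counterpart, changes the wave mix in one arm only. With wave absent from Tables 1 and 1S, such a shift would be neither adjusted for nor visible.

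**Working it through.** **1. The plan's own figure.** Inputs from SAP I.G: "33% OAC initiation rate in the delayed intervention arm", "38% OAC initiation rate in the early intervention arm", "Two-sided type I error rate of 0.05", and 30% attrition. The protocol's table names a continuity-corrected chi-square.

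- Uncorrected n' per arm = [1.960·√(2·0.355·0.645) + 1.282·√(0.33·0.67 + 0.38·0.62)]² / 0.05² = 1,923 at 90% power.
- Corrected n = (n'/4)·[1 + √(1 + 4/(n'·0.05))]² = 1,963. At 95% and 99% power it is 2,418 and 3,401.
- Dividing by 0.70 gives 2,805 / 3,455 / 4,859 per arm, or 5,610 / 6,910 / 9,718 in total. This matches exactly.
- With 10,000 randomized and 30% lost (3,500 per arm), power is 99.2%. At 80,000 it is about 100%. Primary power is not at issue.

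**2. Precision from adding one balanced binary covariate.** The documents give no wave share, wave effect or prior-OAC prevalence, so these are assumed ranges. Marginal rates are held at 33% and 38%, and V is the variance factor for the arm log odds ratio from the expected logistic information: N = (1.960 + 1.282)²·V / (log OR)². Without the covariate, OR = 1.244, V = 2/(0.38·0.62) + 2/(0.33·0.67) = 17.53, and N = 3,854 for 90% power before attrition.

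| Covariate added | Assumed share | Assumed OR with outcome | Arm OR | Fall in N |
|---|---|---|---|---|
| Wave 2 | 20–50% | 0.67–1.5 | 1.245–1.247 | 0.2–0.9% |
| Prior OAC | 10–30% | 2–5 | 1.247–1.285 | 1–13% |

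As a cross-check on a linear scale, variance explained = p(1−p)D²/(0.33·0.67). Wave at 30% share and D = 10 points gives 0.95%. Prior OAC gives 0.9% (10%, 15 points) to 8.5% (30%, 30 points).

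**3. Shift from an unequal wave mix.** Shift = (difference in wave 2 share between arms) × (difference in initiation between waves). Assumed: 1–5 points and 5–10 points.

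- Low: 0.01 × 0.05 = 0.05 points. High: 0.05 × 0.10 = 0.5 points.
- SE of the risk difference with 40,000 per arm = √(2·0.33·0.67/40,000) = 0.33 points. After 30% attrition (28,000 per arm) it is 0.40 points.
- With no true effect and 40,000 per arm, the false-positive rate is Φ(b/SE − 1.96) + Φ(−b/SE − 1.96). At 0.5 points (b/SE = 1.50) it is about 32%. At 0.05 points (b/SE = 0.15) it is about 5%.

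**4. Does a wave term repair arm-specific re-screening?** Suppose, contrary to SAP I.F, that pre-mailing OAC starters stayed in the early arm at sites that did not re-screen wave 2. Assume a wave 2 share of 20–50%, 25–50% of wave 2 not re-screened, a lag of 1–3 months at the 33%-per-year start rate, and all retained starters counted as events. The early arm is then inflated by 0.11–1.60 points (OR 1.005–1.074). The wave-adjusted OR equals the unadjusted OR to within 0.0001 in every scenario, because the error lies between arms inside wave 2. Under the both-arm exclusion as written, the inflation is zero.

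**The case against.** The strongest case against is that wave is balanced in expectation. It rests on pre-randomization provider data, randomization is 1:1 within plan, models are fitted separately by partner, and delayed patients get matching start dates. SAP II says the later exclusions work alike in both arms. The SAP also counts the mailing variations and compares the endpoint with and without a provider letter (Table 4). Most of this stands. It does not cover the mailing requirement, which applies to one arm only; SAP II itself acknowledges that delayed-arm addresses were not assessed.

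Two practical objections also have weight. Some sites had one wave, so a wave term cannot be estimated there; those sites simply drop it. The protocol guarantees only one prior year of coverage, so earlier dispensings are unevenly observed. That limits the covariate but does not rule it out, since Table A's history items work under the same minimum.

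Stronger readings are tempting but unsupported:

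- A reader might infer that discretionary re-screening biases the primary odds ratio and that a wave term would cure it. SAP I.F excludes pre-mailing starters, deaths and disenrollments in both arms, and step 4 shows that a wave term could not cure it anyway.
- A reader might infer that letter content differs by wave. The documents show only that the recipients can differ.
- A reader might take the look-back that "is operationalized as -6000 days from the index AF code" as a long pharmacy history. It defines prior valve, thrombosis and embolism conditions, not dispensings.

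**Conclusion.** The omission is real and worth correcting, but it is minor. Leaving out a covariate that randomization balances does not bias the arm comparison. It costs under 1% of N for wave and about 1–13% for prior OAC use, in a trial whose primary power is already ample.

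The one route to a shift is a wave mix altered by the early-arm mailing requirement, which needs mailability to vary by wave. Its size is 0.05–0.5 points: small beside the planned 5, but up to about 1.5 standard errors at 40,000 per arm. A wave term removes only the part of that selection that runs through wave. The shares, between-wave differences, prevalences and effects behind these ranges are all assumptions.

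**What to change.** - Add wave/pseudo-wave (1 vs 2) to Table A for every partner that mailed in two waves, dropped where it is constant. SAP II.C.1 prescribes one covariate set for all partners, so it needs a sentence allowing this. In the Cox models (II.D.1 and II.D.4), use wave as a stratum.
- Report wave by arm in Tables 1 and 1S. Comparing the two shows whether the post-randomization conditions changed the mix.
- Add OAC dispensing more than 12 months before randomization (yes / no / no look-back beyond 12 months) to the II.C, II.D.1 and II.D.3 models.

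The cost is two more variables in the distributed program and a few table rows. The third category copes only partly with uneven look-back: a patient with a short extra period of coverage and no fill is still coded as no. The change should be written into the SAP before database lock.
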